#### **10.2.2.** Demography and Other Subject Characteristics

Subject demographic information (ie, year of birth, age at consent, sex at birth, reproductive status for female subjects, ethnicity, and race as described by the subject) will be collected at screening.

#### **10.2.3. Prior and Ongoing Therapies**

All medications and procedures conducted within 30 days prior to Screening will be recorded at Screening. Updates to medications or procedures prior to dosing on Treatment Visit 1 should be made as needed.

#### 10.2.4. Medical History/Disease Specific History

A complete medical history of each subject will be collected and documented during screening to determine subject eligibility. The history should include recent blood donations (within 30 days), illnesses, and participation in other investigational drug or device studies.

Disease-specific history to be collected includes date of onset of Raynaud's phenomenon symptoms and first non-RP symptoms relevant to SSc, date of SSc diagnosis, frequency of Raynaud's phenomenon attacks, history of digital ulcers or critical ischemia/gangrene/amputations, and other relevant SSc-RP disease characteristics and history (eg, presence of SSc-specific autoantibodies, nailfold capillaroscopy findings, gastrointestinal dysfunction, other organ involvement).

#### 10.2.4.1. Substance Use

At screening, the amount and duration of tobacco, nicotine, alcohol, and caffeine usage will be collected.

#### 10.2.5. Urinalysis

Urinalysis parameters are identified in Table 2. Results of urinalysis assessments are required for eligibility purposes prior to randomization (Appendix 1).

#### **10.2.6.** Clinical Laboratory Assessments

Clinical laboratory assessments are identified in Table 2. Results of clinical laboratory assessments are required for eligibility purposes prior to randomization (Appendix 1).

#### 10.2.7. Urine Drug Screen

A standard urine drug screen will be performed to determine eligibility prior to randomization (Appendix 1). Subjects who test positive for any drug included in Table 2 will not be eligible for study participation.

#### 10.2.8. Pregnancy Testing

A serum pregnancy test for beta-human chorionic gonadotropin ( $\beta$ -hCG) will be performed on WOCBP at screening to determine eligibility and at each Treatment Visit. At each treatment visit, urine pregnancy tests ( $\beta$ -hCG) will be performed, and a negative result is required to be documented, prior to administration of study treatment. The results of the serum pregnancy test

at each Treatment Visit are not required prior to dosing. If at any point there is a case of a positive urine  $\beta$ -hCG test, the subject will have study treatment interrupted. If the serum test confirms positive, the subject will be discontinued from the study treatment and all the necessary follow up will be conducted as per Section 10.8.6. If the serum test is negative, the subject may resume study treatment.

At Treatment Visit 1, WOCBP will also be provided with a urine pregnancy test that is to be taken at home prior to the subject's Follow-Up visit on the same day of the Follow-Up visit. During the first Treatment Visit subjects will receive adequate training on the use of the home pregnancy test and will be informed on how to properly communicate the results of their test. If the result of the home pregnancy test is positive, subjects will be required to undergo a serum pregnancy test. If the serum test confirms positive, all necessary follow-up will be conducted as per Section 10.8.6. If the serum test is negative, no further follow-up is required.

Women who are surgically sterile or who are postmenopausal are not considered to be of child-bearing potential. Postmenopausal is defined as 12 consecutive months with no menses without an alternative medical cause.

### 10.2.9. Virology Screening

As defined in Table 2, hepatitis C screening will be performed to determine eligibility prior to randomization (Appendix 1).

#### **10.2.10.** Acclimatization Test

Subjects will be required to undergo acclimatization for at least 20 minutes in a temperaturecontrolled room (23  $[\pm 1]$ °C). IR thermography will be used to assess digit temperature to determine eligibility. If a subject's digits do not reach a temperature of at least 27°C, the subject will not be eligible for study participation.

### **10.3.** Pharmacodynamic Assessments

#### 10.3.1. Digital Blood Flow Assessments and Cold Challenges

Assessments of digital blood flow based on both temperature and perfusion and will be conducted simultaneously using IR thermography (Section 10.3.1.1) and LSCI (Section 10.3.1.2), respectively. Digital blood flow data will be analyzed by a central core lab. Details on the applicable instructions regarding the collection, transfer, and analysis of blood flow data will be provided in a separate operation manual. Digital blood flow will be assessed at each Treatment Visit at Predose for 5 minutes at room temperature, and at Postdose prior to cold challenge for 5 minutes at room temperature and for 30 minutes following a cold challenge.

Digital blood flow will be assessed and analyzed as previously described (Wilkinson 2018) and details on the applicable methods can be found in separate operation manuals. Briefly, imaging should be performed at each Treatment Visit at approximately the same time of the day in a temperature-controlled (23 [ $\pm$  1]°C), low-lit room, and any vibrations (included those caused by walking or talking) should be minimized during the digital blood flow assessments. The room temperature should be assessed at least during the acclimatization and re-acclimatization periods, and after the post-cold challenge digital blood flow assessments have been completed. Subjects should be in a seated position during the digital blood flow assessments; standing up and walking

for a minimum of 5 minutes before the start of imaging should be avoided. Hands should be placed at a fixed distance and angle from the thermal camera and LSCI and secured to avoid movement during imaging. Both hands will be used for digital blood flow assessments and cold challenges. Room temperature digital blood flow assessment will be performed following acclimatization for at least 20 minutes. For the cold challenge, hands will be placed in nitrile gloves (to prevent evaporative cooling) and immersed in a temperature-controlled water bath  $(15 [\pm 1]^{\circ}C)$  up to the radiocarpal joints for 1 minute ( $\pm$  3 seconds). The water temperature should be recorded at the beginning and at the end of the cold challenge. Immediately after the cold challenge, the gloves will be removed, the hands will be dried and returned to their original position on the insulating surface, and the post-cold challenge digital blood flow assessment will start 30 ( $\pm$  10) seconds after the end of the cold challenge.

ROIs on both hands will be predefined and the same ROIs will be used for analysis during all digital blood flow measurements for all subjects. Data will be presented in temperature (°C) for IR thermography or in arbitrary pu for LSCI and averaged for all ROIs. Absolute measurements (eg, room temperature values, maximum reduction/recovery) as well as dynamic assessments dependent on the characteristics of the rewarming/reperfusion curve (eg, AUC, time to 50% and 70% recovery [minimum value + (baseline value – minimum value)  $\times$  0.5 and minimum value + (baseline value – minimum value)  $\times$  0.7]) will be assessed.

### **10.3.1.1.** Infrared Thermography

Skin temperature will be assessed using a thermal camera. Imaging software for IR thermography provides quantitative measures of blood flow within predefined ROIs as mean temperature (°C). Additional details regarding the procedures for collection, transfer, and analysis of IR thermography data will be provided in a separate operation manual.

Planned timepoints for IR thermography assessments are provided in the Schedule of Assessments (Appendix 1).

## 10.3.1.2. Laser Speckle Contrast Imaging

Skin perfusion will be assessed using LSCI. Imaging software for LSCI provides quantitative measures of blood flow within predefined ROIs as mean arbitrary pu. Additional details regarding the procedures for collection, transfer, and analysis of LSCI data will be provided in a separate operation manual.

Planned timepoints for LSCI assessments are provided in the Schedule of Assessments (Appendix 1).

### 10.3.2. Visual Analogue Scale for Pain

Subjects will complete a 0 to 100 mm VAS assessment in response to the question "How much pain did you have in your hands after the cold challenge?". The VAS for pain will be completed as specified in the Schedule of Assessments (Appendix 1).

## **10.4.** Urine Drug Screen

A standard urine drug screen for the presence of non-prescribed drugs of interest will be performed at each Treatment Visit as specified in the Schedule of Assessments (Appendix 1).

The results of the urine drug screen are not required prior to initiating study conduct of each Treatment Visit. However, if at any time a subject tests positive for any drug included in Table 2, the subject may be discontinued from study treatment at the discretion of the Sponsor.

## **10.5. Procedures for Blood Draws**

Standard venipuncture may be used for blood collection at Screening. Blood sample collection at Treatment Visits should be performed preferably via venipuncture; however, an indwelling catheter may be used if warranted. If a catheter is used, it should be used consistently for all Treatment Visits for a given subject. The preferred placement of the indwelling catheter is in the antecubital region of the subject's non-dominant arm. The catheter should be placed in the same arm and region of the arm for each Treatment Visit. The method used and the location of the blood draws must be documented at each Treatment Visit.

### **10.6.** Pharmacokinetic Assessments

Blood samples for plasma PK analysis of temanogrel, AR295980, and AR295981 will be collected for all subjects. Blood samples will be obtained as specified in the Schedule of Assessments (Appendix 1). Clock time will be documented for each PK blood sample. Detailed instructions regarding sample collection, processing, and shipping will be provided in a separate laboratory manual.

Collected plasma PK samples may also be stored for up to 3 years after the closing of the study and used for profiling of drug binding proteins, bioanalytical method validation purposes, stability assessments, or to assess other actions of temanogrel (and/or its metabolites) with plasma constituents or for context pertaining to safety events arising during or after the study.

During conduct of each study stage, drug concentration information that may unblind the study will not be reported to investigative sites or blinded personnel.

## **10.7.** Biomarker Assessments

Blood samples for assessment of plasma serotonin concentration and markers of vascular injury and endothelial dysfunction (specified in Table 2) will be collected as specified in the Schedule of Assessments (Appendix 1). Detailed instructions regarding sample collection, processing, and shipping will be provided in a separate laboratory manual.

#### 10.7.1. Future Biomarker Research

Where allowed by the regulatory authorities and if the subject has granted consent, residual plasma from samples collected to measure biomarkers may be stored for up to 10 years after the closing of the study. Samples will be stored according to local regulations for the study at a facility selected by the Sponsor to enable potential future analysis of analytes and biomarkers with the aim to further understand the efficacy, safety, and/or mechanism of action of temanogrel. Tubes will be identified with a barcode using an appropriate label. No diseases/conditions, deoxyribonucleic acid (DNA), or ribonucleic acid (RNA) will be the focus of these analyses. Samples will not be submitted to a public database. The Sponsor and CROs involved in the clinical conduct and analyses of the samples/data will have access to the samples and/or the data that result from the analysis, if performed. By signing the informed consent form

(ICF), subjects agree to the possible future analysis of these samples. At any time, the subjects can contact the clinical staff to request destruction of their residual samples after the required assessments are completed.

### **10.8.** Safety Assessments

Safety assessments will include adverse events, vital signs (Section 10.8.1), physical examinations (Section 10.8.2), ECGs (Section 10.8.3), and clinical laboratory tests (Section 10.8.4). Planned timepoints for all safety assessments are indicated in the Schedule of Assessments (Appendix 1).

#### 10.8.1. Vital Signs

Vital signs measurements will be made in the sitting position and include heart rate, blood pressure, body temperature, and respiratory rate. Subjects should be seated for at least 5 minutes prior to the collection of vital signs. Vital signs will be measured prior to any blood draws that occur at the same study visit or overlapping timepoint, with the exception of the Postdose blood draw for biomarkers and PK (Appendix 2). Planned timepoints for vital signs assessments are provided in the Schedule of Assessments (Appendix 1).

#### **10.8.2. Physical Examinations**

The Investigator will complete the physical exam at Screening. A full physical examination will include the following assessments:

- General inspection
- Head/ears/eyes/nose/throat examination
- Neck
- Cardiac examination
- Auscultation of lungs
- Abdominal examination (liver, spleen, and lower abdomen)
- Neurological assessment
- Musculoskeletal assessment to include lower extremity edema evaluation

A symptom-based physical exam will be performed at the end of the final Treatment Visit.

Focused physical examination of the hands (hand examination) will be performed by the Investigator (or designee) at Screening and at each Treatment Visit for inspection of any active skin ulcerations. If a subject develops an ulcer on their hand during the study, the subject will be discontinued from study treatment and from the study and will follow Early Termination (Section 9.4) procedures.

At each Treatment Visit, the first day of the most recent menstrual cycle will be documented for all women.

Planned timepoints for physical examinations, hand examinations, and menstrual cycle monitoring are provided in the Schedule of Assessments (Appendix 1). In addition, a

symptom-directed physical examination may be performed at the Investigator's discretion at any time during the study.

#### **10.8.3.** Electrocardiography

ECGs will be recorded from a 12-lead ECG machine. ECGs will be captured, recorded, and analyzed according to the ECG Procedure Manual. Parameters to be provided on the confirmed read for each safety ECG are heart rate, RR, PR, QRS, QT, corrected QT interval (QTc), corrected QT interval using Bazett's formula (QTcB), and corrected QT interval using Fridericia's formula (QTcF). All ECGs will be recorded with subjects in supine position. Supine rest time prior to ECGs will be at least 5 minutes. It is recommended to collect ECGs at least 30 minutes after the end of the subject's most recent meal.

The Investigator will be responsible for review and interpretation of ECGs on site for eligibility purposes, and for determining if the ECG is normal, abnormal clinically insignificant, or abnormal clinically significant and recording any clinically relevant worsening from Baseline occurring during the study in the adverse event section of the eCRF. ECGs obtained during Treatment Visits will also be analyzed by the core lab. Both local and central reports must be filed with the source documents.

ECG extractions will be collected during the study as outlined in the Schedule of Assessments (Appendix 1).

#### **10.8.4.** Clinical Laboratory Assessments

Details regarding clinical laboratory sample collection, preparation, and shipment are provided in the laboratory manual. Unless otherwise specified, all laboratory assessments required by the protocol will be performed by a central laboratory. Refer to Table 2 for the list of clinical laboratory tests to be performed and the Schedules of Assessments (Appendix 1) for timing and frequency for each test.

The Investigator must review the laboratory reports, document the review, and record any clinically relevant changes on the adverse event section of the eCRF. The laboratory reports must be filed with the source documents. Clinically significant abnormal laboratory findings are those that are not associated with the underlying disease, unless judged by the Investigator to be more severe than expected for the subject's condition. All laboratory tests with values considered clinically significantly abnormal during participation in the study should be repeated until the values return to normal or Baseline or are no longer considered clinically significant by the Investigator or Medical Monitor.

In cases when laboratory values from nonprotocol-specified assessments are performed at the institution's local laboratory and result in a change in subject management or are considered clinically significant by the Investigator (eg, adverse event or study treatment discontinuation), then the details must be documented in the appropriate eCRF.

## Table 2:Clinical Laboratory Tests

Pregnancy Testing a	Coagulation	Virology Screening				
Serum pregnancy test beta-human chorionic gonadotropin (β-hCG)	Activated partial thromboplastin time (PTT)	e Hepatitis C virus				
Urine β-hCG	Fibrinogen					
	International Normalized Ratio (INR)	)				
	Prothrombin time (PT)					
	Thrombin time (TT)					
Urinalysis	Hematology					
Appearance	Hematocrit					
Bilirubin	Hemoglobin					
Color	Mean corpuscular hemoglobin (MCH	I)				
Glucose	Mean corpuscular hemoglobin concer	ntration (MCHC)				
Ketones	Mean corpuscular volume (MCV)					
Leukocyte esterase	Platelet count					
Microscopic examination of sediment	Red blood cell (RBC) count					
Nitrite	White blood cell (WBC) count with differential					
Occult blood						
рН						
Protein						
Specific gravity						
Urobilinogen						
Serum Chemistry		Endocrinology				
Alanine aminotransferase (ALT)	Phosphorus	Thyroid-stimulating hormone				
Albumin	Potassium	(TSH)				
Alkaline phosphatase (ALP)	bouldin	hyroxine (T4) free				
Aspartate aminotransferase (AST)	Total bilirubin	Triiodothyronine (T3) free				
Bicarbonate	Total cholesterol					
Blood urea nitrogen (BUN)	Total protein					
Calcium	Triglycerides					
Chloride	Uric acid					
Creatinine						
Direct bilirubin						
Creatine kinase (CK)						
Glucose						
Lactate dehydrogenase (LDH)						

Biomarkers
Endothelin-1
Factor VIII activity
Intracellular adhesion molecule 1 [ICAM-1]
Plasminogen activator inhibitor-1 [PAI-1] activity
PAI-1 antigen
Serotonin
Tissue-type plasminogen activator antigen [t-PA]
Vascular adhesion molecule 1 (VCAM-1)
Vascular endothelial growth factor (VEGF)
Von Willebrand factor [VWF]
Urine Drug Screen
Amphetamines, barbiturates, benzodiazepines, cocaine, marijuana, methadone, methamphetamine,

methylenedioxymethamphetamine, opiate, oxycodone, phencyclidine

a Required only for women of child-bearing potential.

#### 10.8.4.1. Clinical Chemistry, Hematology, and Coagulation

Clinical chemistry, hematology, and coagulation parameters that will be assessed during the study are identified in Table 2 and planned timepoints for blood collection are provided in the Schedule of Assessments (Appendix 1).

#### 10.8.5. Adverse Events

#### 10.8.5.1. Definitions

#### **10.8.5.1.1. Adverse Event**

An adverse event is any untoward medical occurrence that does not necessarily have a causal relationship with this treatment. An adverse event can therefore be any unfavorable and unintended sign, symptom, or disease temporally associated with the use of a medicinal product, whether or not considered related to the medicinal product. Adverse events will be collected from the time of consent.

Adverse events can include, but are not limited to, any of the following:

- Unfavorable changes in general condition
- Subjective or objective signs/symptoms
- Concomitant disease or accidents
- Clinically relevant adverse changes in laboratory parameters over the course of the study
- Pre-existing conditions that worsen in severity, increase in frequency, or have new signs/symptoms

#### 10.8.5.1.2. Serious Adverse Event

An adverse event should be classified as a serious adverse event (SAE) if it meets one of the following criteria:

Fatal:	The adverse event resulted in death.
Life-threatening:	The adverse event placed the subject at immediate risk of death. This classification does not apply to an adverse event that hypothetically might cause death if it were more severe.
Hospitalization:	The adverse event required or prolonged an existing inpatient hospitalization. Hospitalizations for elective medical or surgical procedures or treatments planned before the signing of informed consent in the study or routine check-ups are not SAEs by this definition.
Disabling/ incapacitating:	The adverse event resulted in a persistent or significant incapacity or substantial disruption of the subject's ability to conduct normal life functions.
Congenital anomaly or birth defect:	An adverse outcome in a child or fetus of a subject exposed to the study treatment before conception or during pregnancy.
Medically significant:	The adverse event did not meet any of the above criteria but could have jeopardized the subject and might have required medical or surgical intervention to prevent one of the outcomes listed above or involves suspected transmission via a medicinal product of an infectious agent.

#### 10.8.5.1.3. Adverse Drug Reaction

An adverse drug reaction (ADR) in the pre-approval clinical experience with a new medicinal product or its new usages, particularly as the therapeutic dose(s) may not be established, is any noxious and unintended response to a medicinal product related to any dose. The phrase "responses to a medicinal product" means that a causal relationship between a medicinal product and an adverse event is at least a reasonable possibility (ie, the relationship cannot be ruled out).

#### 10.8.5.1.4. Severity

The severity of each adverse event will be assessed at the onset by the Investigator. When recording the outcome of the adverse event the maximum severity of the adverse event experienced will also be recorded. The severity of each adverse event will be graded according to the Common Terminology Criteria for Adverse Events (CTCAE), version 5.0:

Grade 1:	Mild; asymptomatic or mild symptoms; clinical or diagnostic observations only; intervention not indicated.
Grade 2:	Moderate; minimal, local or noninvasive intervention indicated; limiting age-appropriate instrumental activities of daily living (ADL).
Grade 3:	Severe or medically significant but not immediately life-threatening; hospitalization or prolongation of hospitalization indicated; disabling, limiting self-care ADL (eg, preparing meals, shopping for groceries or clothes, using the telephone, managing money).

Grade 4:	Life-threatening consequences, urgent intervention indicated.
Grade 5:	Death related to adverse event.

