## **10.9.** Safety-Related Stopping Criteria

#### **10.9.1.** Bleeding Events

Any bleeding event reported as Bleeding Academic Research Consortium (BARC) 3 or greater will pause enrollment and the event will be reviewed by the Investigator and Medical Monitor. Following review, the event may trigger unblinding, study stop, or the study may resume (following approval by health authorities and IECs/IRBs in accordance with applicable country-specific regulations).

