#### 11.8.2. Adverse Events

Adverse events will be coded using Medical Dictionary for Regulatory Activities (MedDRA). Adverse events will be listed and summarized by system organ class and preferred term, as well as according to severity and relationship to study treatment. Treatment-emergent adverse events (TEAEs) will be summarized by study stage and treatment group. Similarly, bleeding events will be summarized by BARC classification by study stage and treatment group.

For each treatment group, the proportion of subjects with TEAEs will be summarized overall, by severity, and by relationship to study treatment. SAEs will also be summarized by treatment group. A TEAE is defined as:

- An adverse event that occurs after initiation of study treatment that was not present at the time of treatment start.
- An adverse event that increases in severity after the initiation of study treatment, if the event was present at the time of treatment start.

Adverse events occurring before the first dose of study treatment will be summarized separately.

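### Protocol Section 10.8.5.1.4 attaches instrumental-activity examples to the Grade 3 self-care criterion, so Grades 2 and 3 overlap and some moderate events may be graded severe

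*Combined protocol and SAP*

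**What the plan says.** Section 10.8.5.1.4 names the scale and then prints it: "The severity of each adverse event will be graded according to the Common Terminology Criteria for Adverse Events (CTCAE), version 5.0". The five grades follow directly. Two of them use limitation of daily activities as a criterion:

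- Grade 2 includes "limiting age-appropriate instrumental activities of daily living (ADL"; no examples follow.
- Grade 3 opens with "Severe or medically significant but not immediately life-threatening; hospitalization or prolongation of hospitalization indicated" and then adds "disabling, limiting self-care ADL (eg, preparing meals, shopping for groceries or clothes, using the telephone, managing money".

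The same section says that, with the outcome, "the maximum severity of the adverse event experienced will also be recorded".

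The grade reaches the analysis through Section 11.8.2: "For each treatment group, the proportion of subjects with TEAEs will be summarized overall, by severity, and by relationship to study treatment". Nothing else in the protocol or the two notes to file defines either kind of activity or corrects the list.

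**The concern.** On function, the line between moderate and severe depends on the difference between instrumental activities and self-care. The only examples that the scale offers are cooking, shopping, telephone use and handling money. These are household and community tasks, not care of one's own body. They illustrate the Grade 2 criterion but are printed under Grade 3, and no true self-care example is there to correct the impression.

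An investigator who works from the printed page can thus reach either grade for the same event. This touches events that the trial expects: Section 1.2 lists dizziness, headache and tiredness among the effects of single oral doses in healthy volunteers. Any of these could plausibly stop someone shopping or cooking while washing and dressing are unaffected. Safety and tolerability is a secondary objective (Section 2), and the severity breakdown is one of the ways in which it is reported.

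**Working it through.** No sample size, error rate or event rate underlies this point, so there is no figure to reproduce. The check sets the two criteria side by side and then traces where the grade is used.

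**Step 1: grade typical events on each reading.** The first reading uses the criterion terms in their ordinary meaning. The second uses the printed example list.

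| Worst functional effect | By the term | By the examples |
|---|---|---|
| None; mild symptoms | 1 | 1 |
| Cannot shop or cook; washes and dresses normally | 2 | 3 |
| Cannot wash or dress | 3 | 3 |

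The readings part only in the middle row. There the example list moves the grade up, never down.

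**Step 2: look for a correction elsewhere.** There is none. The parenthesis sits inside a complete Grade 3 sentence, so there is no sign that text was displaced when the PDF was read. The abbreviation list expands ADL but does not separate the two kinds.

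**Step 3: trace the use of the grade.**

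- TEAE summaries (Section 11.8.2): used, descriptively, as the proportion of subjects by severity in each treatment group.
- Bleeding rule (Section 10.9.1): not used. "Any bleeding event reported as Bleeding Academic Research Consortium (BARC) 3 or greater will pause enrollment", which is a BARC type and not a CTCAE grade.
- Liver criteria (Section 10.9.2): not used. They rest on ALT or AST, bilirubin, INR and named symptoms or eosinophilia.
- Seriousness (Section 10.8.5.1.2): not used. It has its own list of criteria.
- Efficacy analyses and sample size (Sections 11.2 and 11.5): not used.
- Close-out outputs (Note to File, Amendment 1, Appendix A): no output is titled by severity. Table 4 (TEAE overview) and Listing 5 (TEAE listing) could still show it.

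**Step 4: try to size it.** This would need the number of TEAEs by grade and the share graded on daily activities alone. The documents give neither, so no range can be computed. Zero is possible.

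**The case against.** The strongest reply is that the text does not force the higher grade. CTCAE version 5.0 is named as the governing scale, and an investigator who knows it may ignore the list. Grade 3 also speaks of severe, medically significant and disabling events. A headache that prevents one shopping trip is hard to call disabling, so many investigators would still choose Grade 2. This stands. It turns a claimed shift into a risk of one, and makes disagreement between investigators as likely as a uniform move upward. It does not remove the overlap: the wider Grade 3 wording does not say which grade applies when cooking or shopping is the worst limitation, and the list does.

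A second reply is that treatment comparisons are largely protected. The design is a double-blind crossover, so a misreading would be blind to treatment, and a site would probably apply the same reading in all of a subject's periods. This also stands. No bias for or against temanogrel has been identified.

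A reader might also infer that TEAE counts are inflated, because the TEAE definition in Section 11.8.2 includes a rise in severity. The documents do not support this. A new event is a TEAE at any grade, and a mild pre-existing event that comes to limit shopping has risen in severity whether it is then called Grade 2 or Grade 3.

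**Conclusion.** The example list is attached to the wrong grade, and the printed Grades 2 and 3 overlap as a result. Some moderate events may be graded severe, and grading may differ between investigators. The consequence is confined to descriptive reporting of TEAEs by severity.

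A reader might go further and infer that every event limiting instrumental activities is scored Grade 3, so that severe TEAEs are over-counted. The documents do not show this: they hold no counts by grade, and investigators who follow the terms or the cited scale would not upgrade. Nor does 1/24 = 4.2 percentage points measure the effect. That is the weight of any one subject in a table of the 24 planned for Stage A. It says nothing about how often misgrading occurs, and the number actually treated is not stated.

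The conclusion assumes the ordinary meaning of *instrumental* and *self-care*. The CTCAE text is not among the documents and was not relied on. On that basis the wording error is certain, and its effect on the results is unknown. It is a small correction worth making because it is cheap.

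**What to change.** In Section 10.8.5.1.4, move the parenthesis with the four examples to Grade 2, directly after the instrumental-activities criterion. Under Grade 3, give self-care examples consistent with CTCAE version 5.0, taken from that source. This changes two lines of text, and it matters chiefly if the wording is reused in another protocol.

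For this trial, development was discontinued on 25 August 2022 and the database was locked on 13 October 2022, so site queries are no longer the practical route. Instead, check any Grade 3 TEAE in the listing to see whether it rests only on an instrumental activity, so far as the recorded detail allows. Add a footnote on the wording to any output that shows severity. The Note to File (Amendment 1) already allows changes to output footnotes without a further amendment, so the cost is a short review and one line of text. If there are no Grade 3 TEAEs, nothing more is needed.
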